## **18.2. LABORATORY EVALUATIONS**

Results from the central laboratory will be included in the reporting of this study for clinical chemistry, hematology, and urinalysis Lipid Panel, Thyroid Panel, Coagulation Panel Urine Drug Screening, Serology Panel, and Other Tests.

A list of laboratory assessments to be included in the outputs is included in appendix II/ the protocol, Section 21.

ISAF population will be used for all laboratory summaries. OSAF population will be used for the listings.

Presentations will use standard international (SI) Units

---

Document:

Author:

Version Number:  
Version Date:

Final Draft  
11APR2019

Template No: CS\_TP\_BS016 Revision 4  
Effective Date: 01Apr2016

Reference: CS\_WI\_BS005

Quantitative laboratory measurements reported as “< X”, i.e. below the lower limit of quantification (BLQ), or “> X”, i.e. above the upper limit of quantification (ULQ), will be converted to X for the purpose of quantitative summaries, but will be presented as recorded, i.e. as “< X” or “> X” in the listings.

Note that handling of retests and unscheduled measurements are included in Section 7.3 to save repetition in different sections of the SAP

The following summaries will be provided for laboratory data:

- Actual and change from baseline by visit (for quantitative measurements) and by treatment.
- Shift from baseline by treatment and visit of subject with laboratory values below, within, and above the normal range.
- Incidence of subjects with a Markedly Abnormal Post-Baseline Laboratory value (MAPLV) for select parameters by treatment.
- Actual and change from baseline for selected serum chemistry parameters (Hemoglobin, Haematocrit, Uric Acid and serum prolactin) values by visit, treatment and by gender.
- Shift from baseline by visit, treatment and by gender of subject for selected serum chemistry parameters (Hemoglobin, Haematocrit, Uric Acid and serum prolactin) below, within, and above the normal range.
- Incidence of subjects with a Markedly Abnormal Post-Baseline Laboratory value (MAPLV) for selected serum chemistry parameters (Hemoglobin, Haematocrit, Uric Acid and serum prolactin) values by treatment and by gender.
- Data listings for all laboratory parameters along with comments will be provided. Results outside of the reference range will be flagged.

### **18.2.1. LABORATORY REFERENCE RANGES AND MARKEDLY ABNORMAL CRITERIA**

Quantitative laboratory measurements will be compared with the relevant laboratory reference ranges in SI units and categorized as:

- Low: Below the lower limit of the laboratory reference range.
- Normal: Within the laboratory reference range (upper and lower limit included).

---

Document:

Author:

Version Number:  
Version Date:

Final Draft  
11APR2019

Template No: CS\_TP\_BS016 Revision 4  
Effective Date: 01Apr2016

Reference: CS\_WI\_BS005

- High: Above the upper limit of the laboratory reference range.

In addition to the high and low quantitative laboratory assignments (as identified by means of the laboratory reference ranges), markedly abnormal quantitative safety (and other) laboratory assessments will also be identified in accordance with the predefined markedly abnormal criteria as presented in Appendix 3.

## 18.3. ECG EVALUATIONS

Results from the central ECG (Electrocardiogram) Reading Centre will be included in the reporting of this study. Safety population will be used.

ISAF population will be used for all ECG summaries. OSAF population will be used for the listings.

The following ECG parameters will be reported for this study:

- PR Interval (msec)
- QRS Interval (msec)
- QTcF Interval (msec)
- QTcB Interval (msec)
- QT Interval (msec)
- HR (bpm)
- Overall assessment of ECG (Investigator's judgment):
  - Normal
  - Abnormal, Not Clinically Significant (ANCS)
  - Abnormal, Clinically Significant (ACS)

The following summaries and listings will be provided for ECG data:

- Observed values and changes from baseline will be presented at each evaluation timepoint and by treatment. Data will be summarized using descriptive statistics (n, mean, mean, median, minimum, maximum)

Summary of ECG categories of Markedly Abnormal Criteria will be summarized by timepoint and by

---

Document:

Author:

Version Number:  
Version Date:

Final Draft  
11APR2019

Template No: CS\_TP\_BS016 Revision 4  
Effective Date: 01Apr2016

Reference: CS\_WI\_BS005

treatment in frequency tables with counts and percentages for number of subjects. This will include overall for the oral period and double-blind injection period. The overall oral period includes Day -7, Day -6, Day 1 (Predose) and Baseline and all unscheduled visits within this period. The overall double-blind (DB) injection period includes Day 1 (postdose timepoints) to Day 61 and all unscheduled visits within this period.

- Listing of Electrocardiogram clinical interpretation of ECG findings including Markedly Abnormal Criteria

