14.3.9. Treatment of Missing Data

For analyses of change from baseline, baseline will generally be defined as the predose assessment on Day 1 as scheduled. If this value is unavailable, the last non-missing value prior to dosing will be used. Otherwise, missing observations will be treated as missing at random, and no data imputation will be performed.

Details of incomplete/missing dates for any endpoint will be provided in the SAP.

15. PROCEDURE FOR CLINICAL STUDY QUALITY CONTROL/ DATA COLLECTION, MANAGEMENT, AND QUALITY ASSURANCE

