# **7. GENERAL CONSIDERATIONS**

## **7.1. REFERENCE START DATE AND STUDY DAY**

Study Day will be calculated from the reference start date and will be used to show start/ stop day of assessments and events.

Reference start date is defined as the day of the injection study drug, (Day 1 is the day of the injection study drug) and will appear in every listing where an assessment date or event date appears.

- If the date of the event is on or after the reference date then:

Study Day = (date of event – reference date) + 1.

- If the date of the event is prior to the reference date then:

Study Day = (date of event – reference date).

In the situation where the event date is partial or missing, Study Day, and any corresponding durations will appear partial or missing in the listings.

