## **7.2. BASELINE**

Unless otherwise specified, baseline is defined as the last non-missing measurement taken prior to  
Document:

Author:

Version Number:  
Version Date:

Final Draft  
11APR2019

Template No: CS\_TP\_BS016 Revision 4  
Effective Date: 01Apr2016

Reference: CS\_WI\_BS005

reference start date (including unscheduled assessments). In the case where the last non-missing measurement and the reference start date coincide, that measurement will be considered pre-baseline, but Adverse Events (AEs) and medications commencing on the reference start date will be considered post-baseline.

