### **18.3.1. ECG MARKEDLY ABNORMAL CRITERIA**

Markedly abnormal quantitative ECG measurements will be identified in accordance with the following predefined markedly abnormal criteria

- Absolute values for QTcF and QTcB will be classified as:
  - o Males: > 450 msec or Females: > 470 msec
  - o > 450 msec
  - o > 480 msec
  - o > 500 msec
- Change from Baseline for QTcF and QTcB will be classified as:
  - o > 30 msec increase from baseline
  - o > 60 msec increase from baseline
- Change from Baseline for PR interval will be classified as:
  - o increase in PR interval from baseline > 25% and a PR interval > 200 msec;
- Change from Baseline for QRS interval will be classified as:
  - o increase in QRS interval from baseline > 25% and a QRS interval > 120 msec;
- Change from Baseline for HR will be classified as:
  - o decrease in HR from baseline > 25% and a HR < 50 bpm;
  - o and increase in HR from baseline > 25% and a HR > 100 bpm

---

Document:

Author:

Version Number:  
Version Date:

Final Draft  
11APR2019

Template No: CS\_TP\_BS016 Revision 4  
Effective Date: 01Apr2016

Reference: CS\_WI\_BS005

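### The SAP measures oral-period ECG change against the later pre-injection baseline, so those categories can misstate what changed after the tablets

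*SAP*

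**What the plan says.** SAP 18.3 tabulates the markedly abnormal ECG categories by timepoint and treatment and adds whole-period rows: "This will include overall for the oral period and double-blind injection period". It then lists what goes into the first of these: "The overall oral period includes Day -7, Day -6, Day 1 (Predose) and Baseline and all unscheduled visits within this period". The Day -7 entry is not limited to ECGs after the tablet.

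SAP 18.3.1 gives the criteria. Some are absolute QTc thresholds. The others are relative, such as "> 30 msec increase from baseline" for QTcF and QTcB, with percentage changes for PR, QRS and HR.

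SAP 18.3 and 18.3.1 name no ECG baseline, so the general rule in SAP 7.2 applies: "Unless otherwise specified, baseline is defined as the last non-missing measurement taken prior to" the reference start date. SAP 7.1 fixes that date: "Reference start date is defined as the day of the injection study drug". Protocol 14.3.9 agrees: "baseline will generally be defined as the predose assessment on Day 1 as scheduled". Neither document defines a pre-tablet ECG baseline.

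**The concern.** A row labelled as the oral period and headed increase from baseline will be read as showing what the ECG did after the two 80 mg tablets. Under the rule as written, the Day -7 and Day -6 ECGs all come before the value they are compared with. The result then depends on where the subject stands on Day 1 as well as on what happened after the tablets. The period also contains an ECG taken before any drug, so a pre-tablet reading can be counted as an oral-period event.

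At stake is the accuracy of a descriptive safety table. ECG change from baseline is a listed safety endpoint (SAP 3.3.1). The SAP anchors the oral period to the first tablet for adverse events (18.1) and medications (14), but not for ECGs.

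**Working it through.** **Inputs**

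- ECG times, Protocol Table 2 footnote c: predose and 2 h postdose on Days -7 and -6, then Day 1 predose. None is scheduled on Days -5 to -1.
- Baseline, SAP 7.1 and 7.2 and Protocol 14.3.9: Day 1 predose.
- Criteria: SAP 18.3.1.
- The ECG values below are illustrations. The documents give no ECG data.

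**Timing.** SAP 7.1 numbers pre-injection days as event date minus reference date, so there is no Day 0. Day -7 is 7 days and Day -6 is 6 days before the injection. Every scheduled oral-period ECG except Day 1 predose therefore precedes its baseline by 6 to 7 days.

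**Criteria affected.** SAP 18.3.1 has ten categories. Four are absolute QTc thresholds and do not use baseline. Six do: QTc rise > 30 msec, QTc rise > 60 msec, PR increase, QRS increase, HR decrease and HR increase. The PR, QRS and HR categories also need an absolute threshold to be crossed.

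**Formula.** Let P be the Day -7 predose value, B the Day 1 predose value and x any ECG after the first tablet.

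- SAP change = x - B
- Change since before the tablets = x - P
- So SAP change = (x - P) + (P - B)

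The error is exactly P - B. If Day 1 sits above the pre-tablet value, every oral-period rise is understated by the difference. If it sits below, every rise is overstated.

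**QTcF examples** (msec), in the order Day -7 predose, Day -7 2 h, Day -6 predose, Day -6 2 h, Day 1 predose. The SAP column is the largest x - B over all five ECGs. The last column is the largest x - P over the four ECGs after the first tablet.

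| Pattern | Values | SAP rule | Pre-tablet baseline |
|---|---|---|---|
| Rise washed out by Day 1 | 400, 435, 405, 440, 400 | 440 - 400 = +40, flagged | 440 - 400 = +40, flagged |
| Half persists | 400, 430, 415, 440, 420 | 440 - 420 = +20, not flagged | 440 - 400 = +40, flagged |
| Fully persists | 400, 435, 430, 440, 440 | 440 - 440 = 0, not flagged | 440 - 400 = +40, flagged |
| High pre-tablet value, no rise | 440, 438, 430, 425, 405 | 440 - 405 = +35, flagged | 438 - 440 = -2, not flagged |

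In the second row, P - B = -20, so only a rise above 30 + 20 = 50 msec would be flagged. In the fourth, P - B = +35, so any change above 30 - 35 = -5 msec is flagged. There the post-tablet value of 438 is itself flagged (438 - 405 = +33), so removing the pre-tablet ECG from the period would not cure the problem. The baseline has to change too.

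**PR example** (criterion: > 25% increase and > 200 msec).

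- Persisting rise, 165 pre-tablet, 212 post-tablet, 200 on Day 1: the SAP gives 212/200 - 1 = 6%, not flagged; the pre-tablet baseline gives 212/165 - 1 = 28%, flagged.
- High pre-tablet value, 212 pre-tablet, highest later value 205, 165 on Day 1: the SAP gives 212/165 - 1 = 28%, flagged; the pre-tablet baseline gives 205/212 - 1 = -3%, not flagged.

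**The case against.** The strongest reply is that Days -5 to -1 are meant to wash out oral lurasidone. If they do, Day 1 predose is back at the pre-tablet level, P - B is only measurement noise, and the row works. This stands as far as it goes: the washed-out rise in the table is flagged under both rules, and correctly so. With no carry-over or drift, the two predose ECGs are interchangeable as references and neither rule is the more accurate. It does not rescue the row when Day 1 differs from the pre-tablet level for any reason, and the plan should not need that assumption when a pre-tablet ECG is scheduled.

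Other mitigating points also stand:

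- The absolute QTc rows do not depend on baseline.
- Observed values are summarised at each timepoint and ECG findings are listed.
- The tablets are a tolerability run-in, the objectives concern the injection, and Protocol 14.3.5.3 plans no oral-period row.
- The Baseline record has zero change by construction, so it adds no change-based flag. It is redundant rather than harmful.

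The by-timepoint category rows are not a remedy, because their change criteria use the same baseline.

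A reader might also take SAP 7.2 to bar the Day 1 predose ECG: "In the case where the last non-missing measurement and the reference start date coincide, that measurement will be considered pre-baseline". Baseline would then fall on the Day -6 2 h ECG, an on-drug value, and even the washed-out rise would show 440 - 440 = 0. The wording is loose, but Protocol 14.3.9 names Day 1 predose, so this review does not rely on that reading.

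**Conclusion.** The point holds in a limited form. The six change-based categories, in the overall oral row and the Day -7 and Day -6 timepoint rows, do not measure change from before to after the tablets. They can miss a rise that persists wholly or partly to Day 1, and can count a pre-tablet value that is simply higher than Day 1. For each subject the error is the Day -7 predose value minus the Day 1 predose value.

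A reader might infer more: that ECG rises caused by the tablets are generally missed, or that a given share of subjects would be misclassified. The documents support neither. A washed-out rise is counted correctly, and no within-subject SD, drift or carry-over is given. Any rate would come from assumed values, so none is quoted here.

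The summaries are descriptive, so no alpha, power or sample size is affected. The conclusion rests only on the stated baseline rule and ECG schedule. The msec values illustrate it and are not estimates.

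**What to change.** In SAP 18.3:

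1. For the oral-period change criteria, in both the overall row and the Day -7 and Day -6 timepoint rows, use the last ECG before the first tablet (Day -7 predose) as baseline.
2. In the overall oral-period row, count only ECGs after the first tablet and before the injection. The absolute QTc counts in that row then also exclude the pre-tablet ECG.
3. Drop the redundant Baseline record from that row.
4. Keep the pre-injection baseline for the injection-period rows.

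The cost is a short addition to the text and one extra baseline flag in the ECG dataset. The ECGs are already scheduled, so no new data are needed.

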### **18.3.1. ECG MARKEDLY ABNORMAL CRITERIA**

Markedly abnormal quantitative ECG measurements will be identified in accordance with the following predefined markedly abnormal criteria

- Absolute values for QTcF and QTcB will be classified as:
  - o Males: > 450 msec or Females: > 470 msec
  - o > 450 msec
  - o > 480 msec
  - o > 500 msec
- Change from Baseline for QTcF and QTcB will be classified as:
  - o > 30 msec increase from baseline
  - o > 60 msec increase from baseline
- Change from Baseline for PR interval will be classified as:
  - o increase in PR interval from baseline > 25% and a PR interval > 200 msec;
- Change from Baseline for QRS interval will be classified as:
  - o increase in QRS interval from baseline > 25% and a QRS interval > 120 msec;
- Change from Baseline for HR will be classified as:
  - o decrease in HR from baseline > 25% and a HR < 50 bpm;
  - o and increase in HR from baseline > 25% and a HR > 100 bpm

---

Document:

Author:

Version Number:  
Version Date:

Final Draft  
11APR2019

Template No: CS\_TP\_BS016 Revision 4  
Effective Date: 01Apr2016

Reference: CS\_WI\_BS005

## 18.4. VITAL SIGNS

Vital signs baseline is defined as the pre-injection dose assessment.

ISAF will be used for all vital signs summaries. OSAF will be used for the listings,

The following Vital Signs measurements will be reported for this study:

- [Standing/ Supine] Systolic Blood Pressure (mmHg)
- [Standing/ Supine] Diastolic Blood Pressure (mmHg)
- [Standing/ Supine] Pulse Rate (bpm)
- Respiratory Rate (breaths/min)
- Body Temperature (°C)
- Weight (kg)
- BMI (kg/m^2)

The following summaries will be provided for vital signs data:

- Observed values and changes from baseline will be presented at each evaluation timepoint and by treatment. Data will be summarized using descriptive statistics (n, mean, mean, median, minimum, maximum)
- Incidence of markedly abnormal post-baseline vital sign values (MAPVS) will be presented by treatment
- Listing of Vital Signs.
- Data listing of Markedly Abnormal Post-Baseline Vital Sign Values (MAPVS).

### 18.4.1. ORTHOSTATIC HYPOTENSION

Orthostatic hypotension is defined as a decrease of  $\geq 20$  mmHg in systolic blood pressure or  $\geq 10$  mmHg in diastolic blood pressure upon standing, compared to the systolic and diastolic blood pressures measured in the supine position, respectively.

---

Document:

Author:

Version Number:  
Version Date:

Final Draft  
11APR2019

Template No: CS\_TP\_BS016 Revision 4  
Effective Date: 01Apr2016

Reference: CS\_WI\_BS005

Orthostatic tachycardia is defined as a pulse rate increase of at least 20 bpm and a pulse rate > 100 bpm upon standing, compared to the pulse rate measured in the supine position.

ISAF population will be used for all summaries. OSAF will be used for the listings.

Summary of Subjects with Orthostatic Hypotension, Orthostatic Tachycardia and any Orthostatic hypotension or Orthostatic Tachycardia will be provided. Data will be presented by treatment.

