7.2. Subject Exclusion Criteria

The subjects who meet any of the following criteria will be excluded in the study.

- 1. Subject had an acute exacerbation of psychiatric symptoms requiring change in antipsychotic medication (with reference to drug or dose) within 3 months (90 days) before screening.
- 2. Subject has known or suspected carcinoma.
- 3. Subject has known presence or history of renal or hepatic insufficiency.
- 4. Subject has significant disease(s) or clinically significant finding(s) on physical examination determined by the Investigator to pose a health concern to the subject while on study.
- 5. Subject has a history or presence of clinically significant abnormal ECG (based on ECG central overread report) that may jeopardize the subject's safety to participate in this study, or a screening 12-lead ECG demonstrating any one of the following: heart rate (HR) > 100 bpm, QRS > 120 msec, QTcF > 450 msec, or PR > 220 msec.
- 6. Subject has known history of a severe reaction to a previous antipsychotic (in the Investigator's opinion), including up to 80 mg/day of oral lurasidone.
- 7. Subject has a history of drug-dependence as per DSM-IV-TR criteria during the six month period immediately prior to study entry.
- 8. Subject has known or suspected excessive alcohol consumption, (exceeding more than 4 drinks on any single day or more than 14 drinks per week; 1 drink = 5 ounces of wine or 12 ounces of beer or 1.5 ounces of hard liquor) within 6 months of the screening visit or a positive urine alcohol test at screening.
- 9. Subject answers "yes" to "Suicidal Ideation" Items 4 or 5 on the C-SSRS at screening (in the past 1 month [30 days]) or at any point prior to randomization or history of suicidal behavior within the last two years.
- 10. Subject has significant orthostatic hypotension at screening (ie, a drop in systolic blood pressure of 30 mmHg or more and/or drop in diastolic blood pressure of 20 mmHg or more on standing).

- 11. Subject has presence or history (within the last year) of a medical or surgical condition that might interfere with the absorption, metabolism, or excretion of administered Lurasidone injectable suspension.
- 12. Subject has a history of epilepsy or risk of having seizures.
- 13. Subject has a positive urine alcohol at screening or on Day -12.
- 14. Subject has positive test results within 28 days prior to the start of the study for:
 - a. Human immunodeficiency virus (HIV).

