 - b. Hepatitis B surface antigen and Hepatitis C antibody.
 - c. Urine drug test (marijuana, amphetamines, barbiturates, cocaine, opiates, benzodiazepines, methadone, or other drugs of abuse). However, a positive test for benzodiazepines may not result in exclusion of subjects if the Investigator determines that the use of a prescription benzodiazepine is appropriate.
 - d. Serum β -human chorionic gonadotropin (HCG) consistent with pregnancy (females only).
- 15. Subject has used of any inhibitor or inducer of CYP3A4 taken within 28 days prior to drug administration and until discharge.
- 16. Subject has have used of concomitant medications that prolong the QT/QTc interval within 28 days prior to Day -12 through follow-up.
- 17. Subject has received depot neuroleptics unless the last injection was at least one treatment cycle before Day -12.
- 18. Subject has poor peripheral venous access or does not tolerate venipuncture that would cause difficulty for collecting blood samples.
- 19. Subject has experienced significant blood loss (≥ 473 mL) or donated blood within 30 days prior to screening, or intends to donate plasma or blood or undergo elective surgery during study participation or within 30 days after the last study visit.
- 20. Subject has a prolactin concentration greater than or equal to 200 ng/mL at screening.
- 21. Subject is unwilling to abstain from vigorous exercise from Day -12 until study discharge.
- 22. Subjects has a significant risk of violent behavior or a significant risk of suicidal behavior based on history or in the PI's judgment OR is considered by the Investigator to be at imminent risk of suicide or injury to self, others, or property.
- 23. Subject has a history of allergic reaction (clinically relevant history of drug hypersensitivity) or has a known or suspected sensitivity to any substance that is contained in the study drug or to Polysorbate 80, sodium chloride, or sodium phosphate.
- 24. Subject requires treatment with a drug that consistently prolongs the QTc interval (see Section 22, Appendix IV).
- 25. Subject is currently participating, or has participated in a study with an investigational or marketed compound or device within 30 days prior to signing the informed consent, or

has participated in 3 or more studies within 18 months prior to signing the informed consent.

- 26. Subject is a staff member or the relative of a staff member.

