14.3.5.4. Vital Signs

Body temperature, respiration rate, pulse rate (supine and standing), blood pressure (supine and standing), and weight will be summarized using descriptive statistics at each time point by treatment group. Changes from baseline will be summarized in the same manner. The number and percentage of subjects with Sponsor defined markedly abnormal post-baseline vital sign values (MAPVS) will be presented by treatment.

The number and percentage of subjects with orthostatic hypotension and orthostatic tachycardia will be summarized by treatment. Orthostatic hypotension is defined as a decrease of ≥ 20 mmHg in systolic blood pressure or ≥ 10 mmHg in diastolic blood pressure after the subject had been standing for at least 2 to 4 minutes, compared to the systolic and diastolic blood pressures measured in the supine position, respectively. Orthostatic tachycardia is defined as a pulse rate increase of at least 20 bpm and a pulse rate ≥ 100 bpm after the subject was standing for at least 2 to 4 minutes, compared to the pulse rate measured in the supine position.

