## APPENDIX 3. PREDEFINED MARKEDLY ABNORMAL CRITERIA

### STANDARD ADULT MARKEDLY ABNORMAL POST-BASELINE LABORATORY VALUE (MAPLV) PARAMETERS – SI UNITS

Category		
Parameter Name	Low	High
Age/Gender Restriction, if any		
HEMATOLOGY		
WBC	$\leq 2.8 \times 10^9/\text{L}$	$\geq 16 \times 10^9/\text{L}$
Neutrophils (abs)	$< 0.5 \times 10^9/\text{L}$	$> 13.5 \times 10^9/\text{L}$
Lymphocytes (abs)	N/A	$> 12 \times 10^9/\text{L}$
Monocytes (abs)	N/A	$> 2.5 \times 10^9/\text{L}$
Eosinophils (abs)	N/A	$> 1.6 \times 10^9/\text{L}$
Basophils (abs)	N/A	$> 1.6 \times 10^9/\text{L}$
Neutrophils (relative)	$\leq 0.15$	$> 0.85$
Lymphocytes (relative)	N/A	$\geq 0.75$
Monocytes (relative)	N/A	$\geq 0.15$
Eosinophils (relative)	N/A	$\geq 0.10$
Basophils (relative)	N/A	$\geq 0.10$
Hemoglobin		
Male	$\leq 115 \text{ g/L}$	$\geq 190 \text{ g/L}$
Female	$\leq 95 \text{ g/L}$	$\geq 175 \text{ g/L}$
Hematocrit		
Male	$\leq 0.37$	$\geq 0.60$
Female	$\leq 0.32$	$\geq 0.54$
RBC	$\leq 3.5 \times 10^{12}/\text{L}$	$\geq 6.4 \times 10^{12}/\text{L}$
Platelet Count	$\leq 75 \times 10^9/\text{L}$	$\geq 700 \times 10^9/\text{L}$
SERUM CHEMISTRY		
Sodium	$< 130 \text{ mmol/L}$	$> 150 \text{ mmol/L}$
Potassium	$< 3 \text{ mmol/L}$	$> 5.5 \text{ mmol/L}$
Chloride	$\leq 90 \text{ mmol/L}$	$\geq 118 \text{ mmol/L}$
Calcium	$< 1.75 \text{ mmol/L}$	$\geq 3.1 \text{ mmol/L}$
Phosphate	$< 0.65 \text{ mmol/L}$	$> 1.65 \text{ mmol/L}$

Document:

Author:

Version Number:  
 Version Date:

Final Draft  
 11APR2019

Template No: CS\_TP\_BS016 Revision 4  
 Effective Date: 01Apr2016

Reference: CS\_WI\_BS005

Statistical Analysis Plan

PROTOCOL D1052024  
 Page 60 of 66

Category		
Parameter Name	Low	High
Age/Gender Restriction, if any		
AST (IU/L)	N/A	≥ 3 x ULN
ALT (IU/L)	N/A	≥ 3 x ULN
Alkaline Phosphatase (IU/L)	N/A	≥ 1.5 x ULN
Creatinine	N/A	≥ 177 umol/L
BUN	N/A	≥ 10.7 mmol/L
Total bilirubin (mg/dL)	N/A	≥ 34.2 umol/L OR > 2 x ULN
Total protein	≤ 45 g/L	≥ 100 g/L
Albumin	≤ 25 g/L	N/A
Total-Cholesterol (fasting)	N/A	> 7.76 mmol/L
HDL-Cholesterol (fasting)	< 0.78 mmol/L	N/A
LDL-Cholesterol (fasting)	N/A	> 4.14 mmol/L
Triglycerides	N/A	> 3.42 mmol/L
Uric acid		
Male	N/A	> 595 umol/L
Female	N/A	> 476 umol/L
Glucose (Fasting)	< 2.78 mmol/L	> 13.9 mmol/L
Prolactin	NA	Female: >= 146.0 ng/mL Male: >= 88.5 ng/mL
COAGULATION		
aPTT (sec)	N/A	> 1.5 ULN
INR (ratio)	N/A	> 1.5 ULN
THYROID FUNCTION		
Free T3	< 3.07 pmol/L	> 6.38 pmol/L
Free T4	< 9.65 pmol/L	> 22.5 pmol/L

---

Document:

Author:

Version Number:  

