Table 14.3.2.2	Adverse Events Leading to Study Discontinuation - Injectable Safety Population
Table 14.3.4.1.1	Serum Chemistry: Actual Value and Change from Baseline by Scheduled Timepoint and Treatment - Injectable Safety Population
Table 14.3.4.1.2	Serum Chemistry: Shift from Baseline by Scheduled Timepoint and Treatment - Injectable Safety Population
Table 14.3.4.2.1	Hematology Parameters: Actual Value and Change from Baseline by Scheduled Timepoint and Treatment - Injectable Safety Population
Table 14.3.4.2.2	Hematology: Shift from Baseline by Scheduled Timepoint and Treatment – Injectable Safety Population
Table 14.3.4.3.1	Urinalysis: Actual Value and Change from Baseline by Scheduled Timepoint and Treatment - Injectable Safety Population
Table 14.3.4.3.2	Urinalysis: Shift from Baseline by Scheduled Timepoint and Treatment - Injectable Safety Population
Table 14.3.4.4	Summary of Markedly Abnormal Post-Baseline Laboratory Value (MAPLV) by Treatment - Injectable Safety Population
Table 14.3.5.1	Vital Signs: Actual Value and Change from Baseline by Scheduled Timepoint and Treatment - Injectable Safety Population
Table 14.3.5.2	Summary of Abnormal Post-Baseline Vital Signs (MAPVS) Values by Treatment - Injectable Safety Population
Table 14.3.5.3	Incidence of Orthostatic Hypotension and Orthostatic Tachycardia by Treatment - Injectable Safety Population
Table 14.3.5.4.1	ECG: Actual Value and Change from Baseline by Scheduled Timepoint and Treatment - Injectable Safety Population
Table 14.3.5.4.2	Summary of ECG Categories of Markedly Abnormal Criteria by Treatment - Injectable Safety Population

Document:

Author:

Version Number:  
 Version Date:

Final Draft  
 11APR2019

Template No: CS\_TP\_BS016 Revision 4  
 Effective Date: 01Apr2016

Reference: CS\_WI\_BS005

Statistical Analysis Plan

PROTOCOL D1052024  
 Page 63 of 66

Number	Title
Table 14.3.5.5.1	Summary of Columbia Suicide Severity Rating Scale (CSSRS) by Scheduled Timepoint and Overall Screening/Baseline and Last Visit Questionnaire - Injectable Safety Population
Table 14.3.5.6.1	Investigator Injection Site Reaction by Treatment and Schedule Timepoint - Injectable Safety Population
Table 14.3.5.6.2	Subject Injection Site Reaction Pain by Treatment and Schedule Timepoint - Injectable Safety Population
Figure 14.2.1.1	Mean (+SD) Lurasidone Serum Concentration-time Profiles by Dose on Linear and Semi-logarithmic Scales - Pharmacokinetic Population

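### The orthostatic incidence table (SAP 18.4.1, Table 14.3.5.3) states no post-injection window and no baseline condition, and its tachycardia cut-off differs from the protocol's without being declared.

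*SAP*

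**What the plan says.** Protocol 5.1 and SAP 3.3.1 list orthostatic effects among the safety endpoints to be reported as observed values and changes from baseline.

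The event definition is in Protocol 14.3.5.4: "Orthostatic hypotension is defined as a decrease of ≥ 20 mmHg in systolic blood pressure or ≥ 10 mmHg in diastolic blood pressure". SAP 18.4.1 uses the same 20/10 mmHg, comparing standing with supine. It then states that a "Summary of Subjects with Orthostatic Hypotension, Orthostatic Tachycardia and any Orthostatic hypotension or Orthostatic Tachycardia will be provided", by treatment, in the injectable safety population. The output is Table 14.3.5.3, "Incidence of Orthostatic Hypotension and Orthostatic Tachycardia by Treatment - Injectable Safety Population". None of these places names a time window or a condition on baseline status.

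Exclusion 10 (Protocol 7.2) removes a subject only for "a drop in systolic blood pressure of 30 mmHg or more and/or drop in diastolic blood pressure of 20 mmHg or more on standing", and only at screening.

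The tachycardia definitions differ. The SAP has "Orthostatic tachycardia is defined as a pulse rate increase of at least 20 bpm and a pulse rate > 100 bpm upon standing". The protocol has "Orthostatic tachycardia is defined as a pulse rate increase of at least 20 bpm and a pulse rate" of at least 100 bpm, after 2 to 4 minutes of standing. SAP 4.7 says that no analysis or definition changed from the protocol.

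**The concern.** A table headed by injection dose is read as what happened after the injection. Here the injectable safety population restricts which subjects are counted, but not which of their readings. As written, nothing stops a fall at screening, during antipsychotic washout or 2 hours after an 80 mg tablet from appearing in an injection column.

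A second problem would survive a post-injection window. A subject who habitually falls by 20 to 29 mmHg systolic or 10 to 19 mmHg diastolic is eligible, already meets the definition at entry, and would be counted after injection as well.

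The SAP handles both matters elsewhere. The markedly abnormal vital signs (18.4.2) are post-baseline by name and require a change from baseline for blood pressure and pulse. The ECG categories (18.3) are split into oral and injection periods. Adverse events (18.1) are assigned to periods with a worsening rule. SAP 7.3 does not close the gap, because its post-baseline rule covers markedly abnormal values and best or worst values, not orthostatic events.

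With 6 active subjects per dose, one subject is 1/6 = 16.7 percentage points. A single pre-existing case can therefore change how a dose level looks.

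**Working it through.** The plan gives no figure to reproduce: the sample size is not formally derived and no orthostatic rate is stated. The check compares thresholds, counts readings, and sizes the effect under stated assumptions.

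**1. Overlap of entry and event thresholds.** A subject can be admitted and already meet the hypotension definition with a systolic fall of 20 to <30 mmHg (diastolic fall <20), or a diastolic fall of 10 to <20 mmHg (systolic fall <30). Inclusion 6 allows discretionary exclusion for relevant vital-sign findings but sets no number. No numeric criterion covers standing pulse.

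**2. Scheduled standing readings** (Protocol Table 2, vital-sign row and footnote b).
- Before injection: Screening, Day -12, Day -8, Day -7 (two), Day -6 (two), Day -1, Day 1 predose = 9.
- Of these, after the first oral dose: Day -7 at 2 h, Day -6 predose, Day -6 at 2 h, Day -1, Day 1 predose = 5.
- After injection: Day 1 at 6 h and 12 h, Days 3, 5, 7, 9, 11, 13, 15, 22, 29, 33 and 61 = 13.
- Share before injection: 9/22 = 41%.

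**3. Effect of the window.** Let q be the chance that one reading meets the definition (assumed), with readings independent (also assumed). The chance of being counted is 1 − (1 − q)^22 with all readings and 1 − (1 − q)^13 with post-injection readings only.

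| q | All 22 | Post-injection 13 | Excess, points | Expected per 6 subjects |
|---|---|---|---|---|
| 1% | 0.198 | 0.122 | 8 | 1.19 v 0.73 |
| 2% | 0.359 | 0.231 | 13 | 2.15 v 1.39 |
| 5% | 0.676 | 0.487 | 19 | 4.06 v 2.92 |
| 10% | 0.902 | 0.746 | 16 | 5.41 v 4.47 |

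Across this range, 38% down to 17% of counted subjects would have no qualifying reading after injection.

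**4. Effect of persistent fallers.** Independence does not describe a subject who falls habitually. For that subject the window makes almost no difference; only a baseline condition does. If a proportion c of subjects are persistent fallers (assumed), the chance that a dose group of 6 contains at least one is 1 − (1 − c)^6: 26.5%, 46.9% and 73.8% for c = 5%, 10% and 20%.

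Steps 3 and 4 describe different mechanisms and should not be added. Under independence, conditioning on the single Day 1 predose reading leaves the expected post-injection rate unchanged; its value is for the subjects in step 4.

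**5. Tachycardia.** At-least-100 and above-100 bpm differ only for a standing pulse recorded as exactly 100 bpm. The size is small, but SAP 4.7 is still inaccurate.

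**The case against.** The strongest reply is that the SAP is silent, not wrong. Section 18.4 defines the vital-sign baseline as the pre-injection assessment, and the table is by treatment in injected subjects, so a programmer may well restrict it to post-injection readings. SAP 8 refers to table templates that are not among the documents, and the window could be set there. This stands: a reader might infer that pre-injection readings will be counted, but the text does not say so.

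Other outputs partly cover the gap. Supine and standing values are summarized with change from baseline at each timepoint, and Listing 16.2.8.8 shows subjects with orthostatic change. A reader of groups of 6 could trace individual cases. That lessens the harm, but the incidence count itself remains ambiguous.

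A reader might also take 1 − (1 − q)^9, which is 17%, 37% or 61% at q = 2%, 5% or 10%, as the inflation of the table. It is not. It is the chance of any qualifying pre-injection reading, and many of those subjects also qualify afterwards; the excess in the working is the relevant figure.

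Prolactin may look like the same fault, since entry excludes only "Subject has a prolactin concentration greater than or equal to 200 ng/mL at screening" while the markedly abnormal cut-off is "Female: >= 146.0 ng/mL Male: >= 88.5 ng/mL". It is at most a side note. That count is post-baseline by name, so a predose value alone cannot enter, and change and shift tables by gender are planned. An eligibility limit and a reporting flag need not match.

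Finally, no stopping criterion in Protocol 9.3 refers specifically to orthostatic or prolactin counts, no statistical comparison is planned for safety data, and pooled placebo is treated the same way. All of that stands.

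**Conclusion.** The point holds as a gap in specification and an undeclared change of definition. Table 14.3.5.3 lacks both a post-injection window and a baseline condition, although the endpoint is listed under changes from baseline and entry admits subjects who already meet the hypotension definition.

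If pre-injection readings were counted, the excess would be about 13, 19 or 16 percentage points at q = 2%, 5% or 10%. This rests on assumed rates and independent readings, since the documents give no rates. With a window but no baseline condition, a persistent faller would still be counted, at 16.7 points per subject in a group of 6.

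The documents do not support the stronger conclusions that the SAP counts pre-existing events as injection events or that dose escalation would be misdirected. The consequence is confined to descriptive tolerability reporting. The change is worth making because small dose groups are easily misread and the correction uses data already collected.

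**What to change.** - In SAP 18.4.1 and Table 14.3.5.3, count only readings taken after the Day 1 injection.
- Keep the any-event count. Add a row for subjects who did not meet the definition at the Day 1 predose reading, and state that row's smaller denominator.
- Use the protocol's tachycardia cut-off (standing pulse of at least 100 bpm), or declare the change in SAP 4.7.
- Optional: add a count of subjects newly at or above the prolactin cut-off after injection who were below it at baseline.

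The cost is a few sentences in the SAP and an added row in one table, or two with the prolactin option. No new data are needed. The baseline-free row loses a subject or so from an already small group, which is why the any-event row should stay beside it.
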